## 7.2.1 Blinded independent central review (BICR) procedures

In case of disease progression / treatment discontinuation at the investigator's discretion, or at other time points specified by the sponsor, all imaging films should be submitted to the center for review. Imaging assessment based on RECIST 1.1 and irRECIST will be conducted by two independent imaging experts, assisted by an adjudicator if necessary. Reviewers are blinded to treatment cohorts of subjects.

# 7.3 Exploratory study

In Phase I and Phase II Part 1, an exploratory study of biomarkers will be conducted. Subjects participating in the study should submit archived or the latest formalin-fixed and paraffinembedded (FFPE) tumor tissues or about 20 unstained paraffin sections (if any) during the screening period, which will be sent to the central laboratory designated by the sponsor. Collection, handling, storage and transportation procedures of samples will be addressed in the laboratory manual of the central laboratory. The tumor tissues will be tested as follows:

• Detect immune cell infiltration (including T cell infiltration), expression of PD-1, PD-L1, LAG-3, MHC-II and fibrinoid protein (FGL1) in tumor tissues through immunohistochemistry (IHC).

In addition, blood will be also sampled and tested in Phase I and Phase II Part 1. The peripheral blood will be tested for:

- Cytokines in serum, including but not limited to IFN-γ, IL-2, IL-6, IL-10 and TNF-α.
- Receptor occupancy of MGD013 on PBMC using multiparameter flow cytometer [only limited to phase I];
- Characterization of immune cells using multiparameter flow cytometer, including the
  percentage of B cells, T cells (T cell subsets), NK cells and monocytes in peripheral
  blood and T cell subsets; the markers of T cell activation and / or T cell exhaustion in
  PBMCs and markers of cytolytic activity (including but not limited to PD-1, CTLA-4,
  LAG-3, TIM-3, CD25, CD69 and granzymeB)
  - Exploration of safety-related biomarkers, including but not limited to IFN-γ, IL-2, IL6, IL-10 and TNFa

The above blood analyses will be prioritized based on the degree of subjects' response to drugs

and the number of FFPE sections. In addition, for subjects with immune- and infusion-related reactions or cytokine release syndrome, additional sampling for analysis of serum cytokines. Exploratory study results will be reported separately other than in the clinical study report (CSR).

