#### 2.1.3 Exploratory objective

- To explore the correlation between MGD013/brivanib alaninate-related biomarkers and subject safety, antitumor activity.

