#### 2.2.3 Exploratory objective

- To explore the potential biomarker for MGD013/brivanib alaninate and its correlation with subject safety and antitumor activity.

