## 7.2 Efficacy assessments

Contrast-enhanced CT or MRI of abdomen, pelvic and contrast-enhanced CT of lungs are required at baseline. During the follow-up visit, the same method of radiologic assessment on abdomen, pelvic cavity and other clinically indicated sites should be used. All baseline tumor imaging assessments must be performed within 28 days prior to the start of study medication. If subjects receive scanning before signing an informed consent form, as long as the scanning imaging is within the time limit specified by the protocol, the test method meets the requirements for image collection, and the data are obtained, it can be used for study analysis.

Radiologic examination should be conducted on abdomen, pelvic cavity and other clinically indicated sites every 8 weeks (±7 days) dated from the first day of the first cycle until disease progression. All imaging of Phase II study must be evaluated by independent central review.

Tumor assessment should be carried out in strict accordance with the study plan. If imaging assessment occurs beyond the planned visits and there is no disease progression, subsequent tumor assessments should still be carried out **according to the original plan**.

The investigator will also evaluate imaging response by RECIST 1.1 and irRECIST criteria, and classify the objective tumor response by target lesion assessment into: CR, PR, SD, PD and NE. For the subjects with initial response as PR or CR, the response should be confirmed at an interval of at least 4 weeks. subjects should be administered until PD confirmed according to irRECIST.

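### Blood biomarker assays are prioritised by how the subject responded, so any samples left unassayed would be missing according to the outcome the biomarkers are to be correlated with

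*Combined protocol and SAP*

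**What the plan says.** Section 7.3 provides for exploratory biomarker work: "blood will be also sampled and tested in Phase I and Phase II Part 1". The blood assays listed are serum cytokines, receptor occupancy on PBMC (Phase I only), immune-cell characterisation with activation and exhaustion markers, and safety-related cytokines. The section then gives the rule at issue: "The above blood analyses will be prioritized based on the degree of subjects' response to drugs", and continues "and the number of FFPE sections".

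The purpose of the biomarkers is stated for Phase I in Section 2.1.3: "To explore the correlation between MGD013/brivanib alaninate-related biomarkers and subject safety, antitumor activity". Section 2.2.3 says the same for Phase II Part 1: "To explore the potential biomarker for MGD013/brivanib alaninate and its correlation with subject safety and antitumor activity".

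Table 1 and its footnote 4 schedule the blood samples at Cycle 1 Day 1, Cycle 1 Day 8, Cycle 2 Day 1 and Cycle 3 Day 1, with no selection by response. Tumour imaging is "every 8 weeks (±7 days) dated from the first day of the first cycle until disease progression" (Section 7.2). Section 7.3 adds that the exploratory results will be reported outside the CSR.

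The plan does not define response for the purpose of the priority rule. It does not say whether low-priority samples are eventually assayed, and it sets no minimum assay set. Section 9 contains no biomarker analysis and no adjustment for selective assay; Section 9.3.2 refers to the SAP for analytical detail.

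**The concern.** When a biomarker is to be related to an outcome, the outcome should not decide who has the biomarker measured, unless the analysis is built for that kind of sampling. Here the outcome, or something close to it, ranks subjects for assay.

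If assay capacity or sample runs out before the end of the list, the measured subset is enriched for responders. Response rates by marker level or cut-off would then be too high. Marker distributions would describe the selected subset rather than the treated population. Correlation coefficients, and any comparison of PFS, OS or adverse events by marker, would be distorted too. The distortion could not be corrected later unless the fraction assayed in each response category had been recorded.

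The second criterion raises a separate question. The number of tissue sections has no bearing on whether serum or PBMC can be assayed. Inclusion criterion 3 (Section 4.1) admits subjects on a clinical diagnosis, and Section 7.3 and inclusion criterion 13 ask for tissue only where it exists or applies. Subjects without tissue would rank lower for blood assays for no stated reason.

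**Working it through.** The plan gives no sample size, power or error rate for the biomarker work, so there is no figure of its own to reproduce. The check has three parts: the timing of the rule, the effect on rates, and the effect on association measures. All response rates, assay fractions, prevalences and correlations below are assumptions chosen to show the mechanism; the documents supply none of them.

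**Timing.** The last scheduled biomarker sample is at Day 29 ± 2 days, so by Day 31 (Table 1). The first scheduled scan is 8 weeks ± 7 days from Cycle 1 Day 1, so no earlier than 56 − 7 = 49 days after it. Scheduled collection therefore cannot depend on tumour response seen at a scheduled scan. If the rule refers to tumour response, it can act only on samples already collected.

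**Apparent ORR among assayed subjects.** Let p be the true ORR. Assume all responders are assayed, and a fraction f of non-responders. Then

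apparent rate = p / (p + f(1 − p)).

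- p = 0.15, f = 0.50: 0.15 / (0.15 + 0.425) = 0.15 / 0.575 = 26%.
- p = 0.15, f = 0.25: 0.15 / (0.15 + 0.2125) = 0.15 / 0.3625 = 41%.

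**By marker status.** Take 70 subjects, the evaluable number per Part 1 cohort in the synopsis. Assume half are marker-positive, with a true ORR of 30% in positives and 10% in negatives. Expected counts are 10.5 responders and 24.5 non-responders among 35 positives, and 3.5 and 31.5 among 35 negatives.

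| Non-responders assayed | ORR, marker-positive | ORR, marker-negative | ORR, overall | Odds ratio |
|---|---|---|---|---|
| 100% | 30% | 10% | 20% | 3.86 |
| 50% | 46% | 18% | 33% | 3.86 |
| 25% | 63% | 31% | 50% | 3.86 |
| 0% | 100% | 100% | 100% | not estimable |

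At 50%, for example, the marker-positive rate is 10.5 / (10.5 + 12.25) = 46%. The odds ratio is (10.5 × 31.5) / (3.5 × 24.5) = 3.86. It does not change while some non-responders are assayed, because f multiplies both non-responder counts and cancels. This holds when selection works through response alone.

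**Continuous marker.** A simulation (N = 2,000,000) assumed a true correlation of 0.30 between the marker and degree of response.

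| Subjects assayed | Correlation |
|---|---|
| All | 0.30 |
| Best-responding half | 0.19 |
| Best-responding 20% | 0.15 |
| Best 20% and worst 20% | 0.42 |

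The bias can go either way. With no true association, the correlation stays near 0 under every rule. Response rates by marker status are still inflated: a true 20% in both groups appears as 33% when half of non-responders are assayed (0.20 / 0.60).

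**If selection ignores response.** When everyone is assayed, or a set chosen independently of response, the assumed true values are recovered: 30%, 10% and 20%, and a correlation of 0.30.

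**The case against.** The strongest reply is that the sentence sets an order, not an exclusion. Section 7.3 says without restriction that blood is tested in Phase I and Part 1, Table 1 schedules the same samples for everyone, and nothing says that low-priority samples go unassayed. This stands: outcome-dependent missing data is a possibility that the rule creates, not a fact in the plan. But no passage commits to assaying everything, and a ranking has little purpose if everything is run.

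Response to drugs is undefined and could mean a pharmacodynamic response. Section 7.2, immediately before, uses response for tumour response, so that is the natural reading. The mention of FFPE sections suggests that the sentence may have been meant for tissue assays. It names blood analyses, however, so it needs correcting either way.

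Other objections concern size, and they also stand. The plan reports ORR in the FAS and PPS, not among assayed subjects. The assay fractions are assumed. The odds ratio can survive. Enriching for responders is a legitimate exploratory choice when declared.

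A reader might infer four stronger claims, which the documents do not support:

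- *Subjects without tissue are dropped.* A priority criterion lowers their rank; it excludes nobody.
- *Biased marker results feed into Part 2.* Section 3.1.4 opens Part 2 on at least 6 responders among 30 and on the totality of safety and efficacy data. Section 2.3 gives Part 2 no biomarker objective.
- *Receptor occupancy by dose comes from a response-selected subset.* The documents do not say when that assay is run, and it may be done before the first scan. Nor do they call it the main pharmacodynamic readout of Phase I.
- *The analysis ignores the sampling.* Section 9 has no weighting, but Section 9.3.2 leaves detail to the SAP and no biomarker analysis is set out in the text available, so this cannot be settled.

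**Conclusion.** The concern holds in conditional form. The plan ranks blood assays by a variable at or close to the outcome they are to be correlated with, and it neither guarantees complete assay nor provides for selective assay. If any low-priority samples go unassayed, response rates by marker status are inflated, and marker distributions, correlations, and PFS, OS or adverse-event comparisons by marker are distorted in a direction set by the selection. On the assumed values, an ORR of 15% reads as 26% or 41%, and a correlation of 0.30 reads as anything from 0.15 to 0.42. The effect on PFS, OS and adverse-event comparisons was not quantified. If every sample is assayed, there is no bias.

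The reach is limited to the exploratory objectives of Phase I and Part 1. Primary ORR, safety, DLT decisions and the Part 2 decision are untouched. The point is worth correcting because the rule is explicit and the remedy is cheap, not because the trial's main conclusions are at risk.

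**What to change.** Replace the prioritisation sentence in Section 7.3, and align the laboratory manual, with a rule to this effect:

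*All scheduled blood samples are assayed. If sample or capacity is limited, assays are run in a fixed, pre-specified order that is the same for every subject and independent of response, safety outcome and number of FFPE sections.*

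If the sponsor does want responder enrichment, state it as a case-control or weighted design, pre-specify the analysis, and report the number of subjects assayed in each response category. If the sentence was meant for tissue assays, move it there and reword it.

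Assaying a random subset is a poor alternative. Phase I dose groups hold only 3 to 6 evaluable subjects. At an assumed ORR of 15%, 30 subjects yield about 4 or 5 responders (30 × 0.15 = 4.5), and half-sampling would leave about 2.

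The fixed order costs one sentence and needs no extra samples. Assaying every sample may mean more assays than the sponsor intended; the fixed order is there for that case. The downside of the fixed order is that a few responders with little sample may lack a low-priority assay.

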# 8. Safety Monitoring, Reporting and Management

## 8.1 Definition of adverse event (AE)

In clinical study, adverse event refers to any untoward medical occurrence in a clinical investigation subject administered a investigational product. The event does not necessarily have to have a causal relationship with study treatment. An adverse event (AE) can therefore be any unfavourable and unintended sign (including an abnormal laboratory finding, for example), symptom, or disease temporally associated with the use of an invetsigatonal product, whether or not considered related to the investigational product. Adverse events include serious adverse events (SAE) and non-serious adverse events.

### 8.2 Definition of Serious Adverse Event (SAE)

Serious adverse event refers to an adverse event which occurs during clinical trial and meets any of the following criteria:

- Results in death;
- Is life-threatening (Note: The term "life-threatening" in the definition of "serious" refers to an event in which the subject is at risk of death at the time of the event; it does not refer to an event which hypothetically might have caused death if it were more severe);
- Requires inpatient or prolonged hospitalization (Note: Common usage of "inpatient hospitalization" generally would include being treated by a physician in a hospital for at least a 24 hour period. Emergency room visits that do not result in admission to the hospital should be evaluated for one of the other serious outcomes (e.g., life-threatening; required intervention to prevent permanent impairment or damage; other serious medically important event).);
- Results in persistent or significant disability/malfunction/incapacity;
- Results in congenital abnormality or birth defect;

Other important medical event (defined as an event events that may not be immediately life-threatening or result in death or hospitalisation but may jeopardize the subject or may require medical intervention to prevent one of above listed outcomes. These should also usually be considered serious. Example of such events are intensive treatment in an emergency room or at home for allergic bronchospasm; blood dyscrasias or convulsions that do not result in hospitalisation; or development of drug dependency or drug abuse.). Note: The following scenarios will **not** be reported as SAEs:

- Any results, including death, caused by progressive disease of tumor as assessed by investigator.
- A hospitalization or prolonged hospitalization due to economic issue or for purpose of reimbursement only.
- A hospitalization admission is pre-planned (ie, elective or scheduled surgery arranged prior to the start of the study).

## 8.3 Collection, Record, Follow-up and Report of Adverse Events

### 8.3.1 Time Limit for Collection of Adverse Events

The collecting and recording of adverse events will be throughout the clinical trial, from the

signing of the informed consent form (ICF) to the end of the trial (AE will be collected until 30 days after the last dose of investigational drugs). AEs and SAEs that occur following the signing of the ICF but before the first dose treatment should be recorded on Medical History page of eCRF form as pretreatment symptoms and signs, and not collected as AEs on the AE eCRF page, but if deteriorates (higher than a grade) after administration the investigational drug, such events should be recorded as AEs

## 8.3.2 Follow-up of Adverse Events

Investigators must follow up all adverse events until their disappearance or recovery to baseline, up to disease stable in case of permanent injury; if an adverse event is not recovered at the last visit of the study, investigators must continue to follow up the adverse event until disappearance or recovery to baseline level, or clinical stability. Subsequent follow-up may not be recorded in the eCRF, but the sponsor has the right to ask investigators to provide more information where necessary.

### **8.3.3** Elements of Adverse Event Collection

- Selection of AE term: The disease diagnosis is preferred as AE term if a unifying diagnosis is available; if not, the associated symptoms and signs are to be captured and recorded using standard medical terminology. Once the diagnosis is confirmed with the follow up information, the symptoms and sign should be replaced with diagnosis accordingly. One single event term to be recorded should only contain a sole event, such as a single diagnosis, sign and/or symptom. For example, if a subject experiences "vomiting and diarrhea", then it need to be captured separately as two AEs rather than one, namely "vomiting" and "diarrhea".
- Onset date/Stop date of AE: In general, the date when first signs and/or symptoms appear is captured as onset date rather than the time of confirmed diagnosis, to prevent missing safety information or underestimating safety hazards. If the date when first signs and/or symptoms appear cannot be determined based on the available information, then the time of disease diagnosis will be used as the event onset date.
- AE severity (CTCAE Grade 1-5): AE severity is graded from 1 to 5 according to the Common Terminology Criteria for Adverse Events (CTCAE 5.0); for those reported without assigned CTCAE Grade, the terms including "mild", "moderate" and "severe" that used to describe the event severity can be converted to the corresponding CTCAE Grade by referring to the defined CTCAE criteria. Serious adverse events (SAEs) are different from severe AEs: SAEs are determined based on clinical outcome or medical intervention as described in Chapter 8.2, while the severity of AE refers to the event intensity which is usually evaluated and graded according to the CTCAE. A severe AE is not necessarily an SAE, e.g. nausea lasting for several hours may be graded as severe in CTCAE grading however probably not a SAE. Conversely, a stroke that caused partial disability may only be mild based on CTCAE grading; however, it is generally reported as a SAE.
- The investigator should evaluate and provide causal relationship between the investigational drug and the AE, for the details please refer to 8.3.4.
- Action taken with the investigational drug in response to AEs (e.g., whether the AE led to drug discontinuation or dose reduction, etc.).

- Concomitant medication: It should be indicated whether the concomitant medication is for treatment of a specific AE/SAE, or part of clinical routine diagnosis and treatment, which should be clarified and recorded in the SAE report.
- Event outcome: Outcomes of AE include complete recovery, events not yet resolved, recovery with sequelae, death and unknown.

## **8.3.4** Causality Assessment

The investigator's assessment of causality must be provided for all AEs to determine if there is a reasonable possibility that the investigational product caused or contributed to an AE. "Yes" or "No" will be provided. Generally, the following factors should be considered in performing causality assessment:

- Temporal relationship with investigational drug treatment;
- Whether the symptoms and signs are consistent with the pharmacological action of the drug's active ingredients;
- Alternative medical reasons other than the investigational drug treatment;
- De-challenge results; if symptoms/signs relieved or improved upon reduction or withdrawal of the investigational drug;
- Re-challenge results; if symptoms/signs recurred or worsened upon re-introduction of the investigational drug treatment;
- Evidence of previous, similar incidents from literature search.

In case of insufficient information which does not allow for a comprehensive assessment, the AEs could be conservatively assessed as related to the investigational drug and the reason need to be documented.

## 8.3.5 Adverse Events based on Laboratory Examinations and Tests

The laboratory test, vital signs, ECGs and any other safety relevant test specified in the study will be summarized in the clinical study report. The change of value from the baseline is reported as an AE only if it is medically significant. For example, worsened by 1 grade or higher in CTCAE grading, led to discontinuation, dose adjustment or interruption of study treatment or the investigator believes that this abnormality should be reported as an AE.

When the abnormal findings in laboratory test/examinations, vital signs, ECG and other safety relevant test are considered related to a clinical diagnosis, then only this clinical diagnosis need to be reported as AE and those abnormal findings are handled as additional safety information related to the corresponding diagnosis. In this case, the investigator should use clinical terminology (e.g. anemia) rather than laboratory terminology (e.g. hemoglobin decreased) as applicable.

### **8.3.6 Progressive Disease**

Events due to progression of the neoplasm disease which under investigation should not be reported as AEs or SAEs.

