#### **Study Design**

This is a multicenter, open-label, phase I/II clinical study. This study consists of two phases: the dose escalation study (Phase I) and the dose expansion study (Phase II). Phase II study will consist of two parts: Part 1 and Part 2.

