#### Hepatic Events

The most common hepatic events were laboratory test abnormalities in liver enzymes (e.g. AST, ALT) and bilirubin. Since a majority of subjects treated with brivanib alaninate were reported with elevated liver enzymes or bilirubin (≥ CTCAE Grade 1), liver function should be monitored regularly throughout the study and dose interruption or reduction should be considered if abnormalities ≥ CTCAE Grade 3 occur.

As indicated by phase III studies in HCC patients, clinically important events of hepatic encephalopathy (4.6% vs.1.5%), hepatic failure (3.1% vs.1.5%), and acute hepatic failure (0.4% vs.1.5%), though slightly more common for brivanib alaninate than placebo, occurred infrequently.

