### 8.3.9 Adverse Event of Special Interest (AESI)

Given the mechanism of action and summary of the aggregate data from a set of preclinical and clinical studies previously conducted, the event listed as follows are selected as AESIs of brivanib alaninate in this trial:

- Important identified risks: hypertension, RPLS, hepatic events, hypothyroidism, hyponatremia, proteinuria, arterial thrombotic events;
- Important potential risks: hemorrhage, venous thrombotic events, left ventricular dysfunction, gastrointestinal perforation, and impaired wound healing;

If an AESI meets SAE criteria, then it should be reported as such according to the standard SAE reporting procedure as specified in protocol. Otherwise, AESIs will be recorded on eCRF only for periodic review and analysis by the sponsor.

AESIs of MGD013 include ≥Grade 3 infusion-related reactions and any immune-related adverse events (irAEs) leading to discontinuation and interruption of MGD013. See 8.4.1.

All occurrences of AESIs of MGD013 must be reported to the Sponsor within 24 hours of awareness. The investigator should complete the "AESIs Report Form" within 24 hours of awareness and report the events to the sponsor by email. If an AESI meets SAE criteria, then it should be reported directly in accordance with standard SAE reporting procedures as specified.

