## 9.2 Sample Size Determination

During Phase I monotherapy dose escalation study, the starting dose group (MGD013 120 mg Q2W) will adopt single-subject dose escalation and one subject will be enrolled. Subsequent dose groups and combination treatment will adopt the traditional 3+3 dose escalation scheme, with 3 - 6 evaluable subjects each, 30 - 43 subjects in total.

Phase II Part 1 is a single-arm, SWOG two-stage design study with ORR as its primary efficacy endpoint.

40 subjects are needed
There are 2 stages for the 2nd line cohort and the radiological response (according to RECIST1.1 criteria) of 3 and more out of 20 evaluable subjects at the first stage will support the decision to proceed to the second stage of subject accrual until there are 40 evaluable subjects in this cohort.

Assuming the dropout rate is 10%, 34 subjects will be enrolled.

Similarly, the study has two stages. In the first stage, if response (according to RECIST 1.1 criteria) is observed radiologically in 1 or more out of 15 evaluable subjects, the enrollment of second stage will be open and an additional of 15 evaluable subjects will be enrolled. Assuming the dropout rate is 10%, 45 subjects will be enrolled.

Phase II Part 2 is a expansion study and it is estimated to enroll 120 subjects to further assess the safety and efficacy of the investigational drug.

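### Sections 8.2 and 8.3.6 keep events that the open-label investigator attributes to tumour progression out of the AE and SAE data, so non-fatal hepatic failure, encephalopathy and bleeding can be missing from the safety summaries

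*Combined protocol and SAP*

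**What the plan says.** Section 8.3.6 reads, in full: "Events due to progression of the neoplasm disease which under investigation should not be reported as AEs or SAEs". Among the scenarios not to be reported as SAEs, section 8.2 lists: "Any results, including death, caused by progressive disease of tumor as assessed by investigator". Section 8.3.7 adds that a death caused by progression goes to the monitor at the next visit and into its own eCRF module, but is not an SAE. Deaths of unclear or unknown cause are SAEs.

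Section 8.3.9 names the brivanib AESIs. They begin with "Important identified risks: hypertension, RPLS, hepatic events, hypothyroidism, hyponatremia, proteinuria, arterial thrombotic events", and haemorrhage follows as an important potential risk. AESIs that are not serious are still to be recorded in the eCRF. No sentence says whether 8.3.6 or 8.3.9 prevails when a hepatic event or a bleed is blamed on progression.

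The setting is unblinded and uncontrolled: "This is a multicenter, open-label, phase I/II clinical study", and "Phase II Part 1 is a single-arm, SWOG two-stage design study with ORR as its primary efficacy endpoint". The one blinded element is central imaging review (7.2.1), where "Reviewers are blinded to treatment cohorts of subjects". It does not cover safety events.

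**The concern.** In advanced liver cancer, hepatic failure, encephalopathy and bleeding can come from the tumour or from treatment. Hepatic events are an identified risk of brivanib and haemorrhage a potential one (1.1.4.2.3, 8.3.9). For MGD013, of these event types, the first-in-human data show hepatic toxicity only: immune-mediated hepatitis, and raised ALT with raised bilirubin, among the related SAEs (1.1.3.2). Section 8.4.3 names hepatotoxicity as a possible overlapping toxicity of the combination.

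The exclusion acts when data are collected. Section 8.3.4 asks whether the product caused or contributed to an AE, but an event set aside as progression never becomes an AE, so that question is not put. Safety is a primary objective in Phase I and in both parts of Phase II, and no control arm exists against which unusual attribution would show. The first-in-human study was more inclusive: section 1.1.3.2 lists a lung haemorrhage among SAEs put down to the underlying tumour or concomitant disease. A difference in recording of that kind makes comparison across studies harder.

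**Working it through.** **1. What happens to each kind of information**

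- *Non-fatal clinical event attributed to progression.* Not an AE or SAE (8.3.6). The section 9.3.1 summaries count AEs, DLTs, AEs leading to withdrawal, discontinuation or death, and SAEs, so the event appears in none of them. No separate listing is planned.
- *Death attributed to progression.* Recorded in the eCRF (8.3.7) and counted in overall survival. Section 9.3.1 summarises only AEs leading to death and plans no table of all on-treatment deaths.
- *Laboratory change.* Summarised whatever the attribution (8.3.5), with before-and-after tables and listings (9.3.1). Where a laboratory finding belongs to a clinical diagnosis, however, 8.3.5 has only the diagnosis reported as the AE, and 8.3.6 may then remove that diagnosis.
- *DLT.* Section 3.1.3 requires at least possible relatedness. An event blamed on progression would normally fail that test anyway, so the further effect of 8.3.6 is limited.

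**2. Whether imaging can support the attribution**

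The first scheduled post-baseline scan is at 8 weeks ± 7 days (7.2), and the DLT window is 28 days (3.1.3). For early events, attribution to progression will normally rest on clinical judgement. Neither 8.2 nor 8.3.6 asks for more than that.

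**3. Illustration of size**

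No design figure of the plan rests on this rule. The inputs are:

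- Part 2 size n = 120 (9.2).
- Brivanib rates p, against placebo, from the Hepatic Events part of 1.1.4.2.3: encephalopathy 4.6% against 1.5%, hepatic failure 3.1% against 1.5%. That text gives no denominators, so the rates are taken as fixed.
- f, the share of these events attributed to progression. **This is an assumption.** The documents give no value, so a range of 0% to 75% is shown.

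Recorded rate = p × (1 − f). Expected recorded count = n × p × (1 − f). The chance of recording at least three events is the exact binomial tail at the recorded rate.

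With f = 0: 120 × 0.046 = 5.52 and 120 × 0.031 = 3.72.

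| f | Encephalopathy: rate | count | P(≥3) | Hepatic failure: rate | count | P(≥3) |
|---|---|---|---|---|---|---|
| 0% | 4.6% | 5.5 | 0.918 | 3.1% | 3.7 | 0.722 |
| 25% | 3.5% | 4.1 | 0.787 | 2.3% | 2.8 | 0.530 |
| 50% | 2.3% | 2.8 | 0.523 | 1.6% | 1.9 | 0.285 |
| 75% | 1.2% | 1.4 | 0.161 | 0.8% | 0.9 | 0.067 |

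The share at which the recorded rate equals the placebo rate is 1 − 1.5/p. For encephalopathy this is 1 − 1.5/4.6 = 67%. For hepatic failure it is 1 − 1.5/3.1 = 52%.

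In the Part 1 combination cohort (30 + 40 = 70 evaluable subjects), 70 × 0.046 = 3.2 encephalopathies and 70 × 0.031 = 2.2 hepatic failures are expected at f = 0. At f = 50% these become 1.6 and 1.1.

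**The case against.** The strongest reply is that much of the safety information survives. All deaths during the study and within 30 days of last dose must be reported, and those of unclear cause are SAEs. Biochemistry is scheduled on Day 1 of each cycle from Cycle 2, with further Day 8 tests in Cycles 1 and 2, and is tabulated without regard to attribution. Haemorrhage of Grade 3 or above is listed in 4.3.1 as a reason for permanent discontinuation, with no relatedness condition, so a serious bleed leaves another trace. All of this stands. It narrows the loss to non-fatal clinical events and lesser bleeds, but does not restore them.

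It can also be said that AESIs are a subset of AEs, so 8.3.6 decides what enters and 8.3.9 only classifies it. On that reading there is no contradiction, but a hepatic event or bleed blamed on progression then goes unrecorded as an AESI. The order of precedence needs stating either way.

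The illustration has real limits. The brivanib rates bear on Part 2 only if the combination is selected; 3.1.4 allows MGD013 alone. The same text reports acute hepatic failure *lower* on brivanib (0.4% against 1.5%) and calls these events infrequent, so the excess is not uniform. The share attributed to progression is unknown.

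Finally, recording these events will not remove the open-label investigator's judgement: the same person would still answer the causality question. That is correct. The gain is in the completeness of all-cause counts, which would then include some true progression.

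**Conclusion.** The point holds as a gap in data collection. Under 8.3.6, read with 8.2, non-fatal clinical hepatic events, encephalopathy and bleeding can be left out of the AE, SAE and AESI data on the investigator's attribution alone, without imaging support and without a causality judgement.

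A reader might infer more than the documents support:

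- *That fatal toxicity vanishes.* Section 8.3.7 keeps every death in the data; what is missing is a table of them.
- *That DLT counts are seriously compromised.* Section 3.1.3 already requires possible relatedness.
- *That the known hepatic signal would disappear.* This depends on the assumed share. At 50%, recorded hepatic failure (1.6%) is near the placebo rate, but encephalopathy (2.3%) is still about one and a half times it.
- *That reported hepatic toxicity must be biased downward.* Removing an event that truly was progression loses nothing from a toxicity estimate, and the documents do not show how attributions would divide.
- *That the choice of Part 2 treatment is distorted.* Under 3.1.4, safety and efficacy data together decide between the treatments when both reach six responders, and the rule applies to both cohorts.
- *That bleeding and encephalopathy are known risks of both drugs.* Haemorrhage is a potential risk of brivanib, encephalopathy is reported for brivanib, and for MGD013 the evidence among these events is hepatic only.

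The figures show the mechanism under a stated range. They do not estimate what would be lost.

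**What to change.** - In 8.2, 8.3.6 and 8.3.7, limit the exemption to the term *disease progression* itself, and to death reported only under that term, when progression is radiographically documented.
- Record clinical hepatic events, encephalopathy, ascites and bleeding as AEs, or as SAEs where the criteria are met, with the 8.3.4 causality judgement and a flag for suspected progression.
- State that the AESI rule in 8.3.9 prevails over 8.3.6.
- Add to 9.3.1 a table of all deaths within 30 days of last dose by attributed cause, from data that 8.3.7 already collects.

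The cost is more AE and SAE entries and a less favourable all-cause safety table. No visit or procedure is added. With the flag, hepatic counts can be shown with and without events of suspected progression, so the added noise from true progression is visible to the reader.
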